COVER PAGE SU-G-01 TRIAL PROTOCOL

Official trial title	A randomised, parallel-group, double-blind, placebo-controlled phase III trial assessing the efficacy and safety of 5-grass mix SLIT-drops in adults with grass pollen-induced rhinoconjunctivitis
NCT number	NCT04881461
Document date	12-Nov-2021

Clinical trial protocol Trial ID: SU-G-01

A randomised, parallel-group, double-blind, placebo-controlled phase III trial assessing the efficacy and safety of 5-grass mix SLIT-drops in adults with grass pollen-induced rhinoconjunctivitis

Sponsor: ALK-Abelló A/S [name]

Investigational medicinal product: 5-grass mix SLIT-drops

Phase: III

Regulatory trial identifier number(s):

EudraCT No: 2020-000455-12

Document status: Final

Date: 12-Nov-2021

Version number: 4.0

Property of ALK

May not be used, divulged, published or otherwise disclosed without the written consent of ALK

Clinical trial protocol Trial ID: SU-G-01	Date: Version:	12-Nov-2021 4.0	
EudraCT No. 2020-000455-12	Status:	Final	
CONFIDENTIAL	Page:	2 of 77	

Protocol synopsis

Trial ID	SU-G-01
EudraCT no.	2020-000455-12
Title of trial	A randomised, parallel-group, double-blind, placebo-controlled phase III trial assessing the efficacy and safety of 5-grass mix SLIT-drops in adults with grass pollen-induced rhinoconjunctivitis
Main objectives	Primary objective:
	 To compare the efficacy of 5-grass mix SLIT-drops to placebo in relieving grass rhinoconjunctivitis symptoms and in use of symptom-relief medication during the 2nd Peak Grass Pollen Season (PGPS)
	Key secondary objectives:
	• To measure the impact of treatment with 5-grass mix SLIT-drops compared to placebo on health-related quality of life as a result of grass pollen-induced rhinoconjunctivitis during the 2nd PGPS
	 To compare the efficacy of 5-grass mix SLIT-drops to placebo in relieving grass rhinoconjunctivitis symptoms and in use of symptom-relief medication during the 1st PGPS
	• To measure the impact of treatment with 5-grass mix SLIT-drops compared with placebo on health-related quality of life as a result of their grass pollen-induced rhinoconjunctivitis during the 1st PGPS
Primary estimand	The primary estimand is the absolute difference between the 5-grass SLIT-drops and placebo treatment policies based on the average total combined score (TCS) during the 2nd PGPS in the population is defined by the trial inclusion and exclusion criteria, in the hypothetical situation that all subjects complete treatment for the planned duration.
Secondary estimand	The secondary estimand is the absolute difference between 5-grass SLIT-drops and placebo treatment policies based on the average TCS during the 2nd PGPS, in a population defined by the trial inclusion and exclusion criteria, regardless of whether subjects complete treatment for the planned duration.
Primary endpoint	The primary efficacy endpoint is the average daily allergic rhinoconjunctivitis TCS during the 2nd PGPS
Secondary endpoints	The average weekly overall rhinitis quality of life questionnaire (RQLQ) score during the 2nd PGPS
	• The average daily allergic rhinoconjunctivitis TCS during the 1st PGPS

Clinical trial protocolDateTrial ID: SU-G-01VerEudraCT No. 2020-000455-12StateCONFIDENTIALPage	te: 12-Nov-2021 rsion: 4.0 tus: Final ge: 3 of 77
--	--

	The average weekly overall RQLQ score during the 1st PGPS
Trial design	A phase III randomised, parallel-group, double-blind, placebo-controlled trial of 5-grass mix SLIT-drops in adults with grass pollen-induced moderate to severe allergic rhinoconjunctivitis, with or without asthma, conducted over two grass pollen seasons
	All randomised subjects should receive daily treatment continuously from at least 16 weeks before the anticipated start of the 1st entire grass pollen season (EGPS) through the 2nd EGPS, corresponding to approximately 26 months of treatment At least 9 in-clinic visits and up to 3 phone contacts are planned for each subject
Main assessments	Efficacy assessments: Rhinoconjunctivitis symptoms assessment (Nose symptoms; runny nose, blocked nose, sneezing, itchy nose; Eye symptoms; gritty feeling of the eyes, red/ itchy eyes and watery eyes) Rhinoconjunctivitis rescue medication
	Safety assessments: Adverse events Clinical laboratory tests Vital and clinical signs
Main criteria for inclusion	 Male or female aged ≥18 years on the day informed consent is obtained
	A clinical history of grass pollen-induced allergic rhinoconjunctivitis for two years or more with or without asthma
	• A clinical history of severe allergic rhinoconjunctivitis symptoms (interfering with usual daily activities or sleep) induced by grass pollen, which remain troublesome despite symptomatic treatment with antihistamines, nasal steroids or eye drops during the previous grass pollen season
	 Positive specific immunoglobulin E (IgE) (defined as ≥class 2, ≥0.70 kU/I) against grass: Phleum pratense
	Positive skin prick test to Phleum pratense at screening
Main criteria for exclusion	• Has a clinically relevant history of symptomatic seasonal and/or perennial allergic rhinoconjunctivitis and/or asthma caused by an allergen other than grass pollen, to which the subject is exposed, which could potentially overlap with the efficacy assessment periods

Clinical trial protocol Trial ID: SU-G-01 EudraCT No. 2020 000455 12	Date: Version: Status:	12-Nov-2021 4.0 Final	Κ
Eudrac 1 No. 2020-000455-12	Status:	Final	
CONFIDENTIAL	Page:	4 of 77	

	• Within the last 3 months before the randomisation visit, has had an occurrence of any clinical deterioration of asthma that resulted in emergency treatment, hospitalisation, or treatment with systemic corticosteroids
	• SLIT treatment with any grass pollen AIT for more than 1 month within the last 5 years. In addition, any SLIT treatment with grass pollen AIT within the previous 12 months
	• SCIT treatment with any grass AIT reaching the maintenance dose within the last 5 years. In addition, any SCIT treatment with grass AIT within the previous 12 months
	Ongoing treatment with any allergy immunotherapy product
	Uncontrolled or severe asthma requiring daily use of more than 800 mcg budesonide or equivalent at screening
Investigational medicinal products	ALK 5-grass mix SLIT-drops
	The 5-grass mix SLIT-drops contains 5 different grass species: Dactylis glomerata L (cat grass / cock's foot / orchard grass), Phleum pratense L. (timothy), Lolium perenne L. (ryegrass), Anthoxanthum odoratum L (sweet vernal / vernal grass), Poa pratensis L. (Kentucky bluegrass)
	The treatment schedule for the allergens included in this trial will be as follows:
	 Initiation: 50 SRU/day for five consecutive days followed by 150 SRU/day for five additional consecutive days Maintenance: 300 SRU/day (once a day) from day 11
	The investigational treatment must be taken continuously during the trial
Duration of treatment	Treatment will be initiated after the end of the entire 2021 grass pollen season and will continue until the end of the 2023 entire grass pollen season corresponding to approximately 26 months of treatment
Number of subjects to be enrolled	440 subjects to be randomised
Number and distribution of trial sites	Estimated 50-65
Statistical methods	Statistical analyses will be performed using SAS software, version 9.4 or later (Cary, North Carolina, SAS Institute Inc.). All efficacy analyses will be performed based on the full analysis set employing hierarchically testing to control the family-wise error rate at 5% level. All endpoints will be tested on a 5% significance level, and all tests and confidence intervals will be 2-sided.

Clinical trial protocol Trial ID: SU-G-01	Date: Version:	12-Nov-2021 4.0		
EudraCT No. 2020-000455-12	Status:	Final		
CONFIDENTIAL	Page:	5 of 77		

	Using the framework proposed in the ICH E9(R1) addendum, two estimands are defined: primary estimand - trial product estimand and secondary estimand - treatment policy estimand. The main estimator and sensitivity estimator(s) for both estimands will be based on an identical method of statistical analysis, although the actual data used in each analysis may vary according to the different strategies taken for the handling of IEs and missing data.
	The absolute treatment difference between two treatments will be estimated based on the full analysis set by using model of Mixed Model of Repeated Measurements with relevant endpoint in 1st year and in 2nd year as the response variables, treatment, visit number, interaction of treatment and visit number and asthma indicator as fixed variables and trial site as a random class effect. The estimated difference in adjusted means between the two groups will be presented together with the associated 2-sided 95%-confidence interval and the p-value for the test of no difference.
	Missing data will be imputed using method of unrestricted random sampling with replacement. The average score will be imputed, but not the daily/weekly values. Rubin's multiple imputation strategy with 1000 imputations will be used. Seed used for imputation will be 12345.
	Safety evaluation will include description of AEs, and descriptive data analysis of laboratory assessments, and vital signs. The safety evaluation will be based on the safety analysis set (all randomised subjects who received at least one dose of IMP).

Table 10	Symptom relieving medication for rhinitis with/without conjunctivitis	61
Table 11	Summary of MMRM response variables	62

List of appendices

Appendix 1: Protocol signature page Appendix 2: Investigator agreement on clinical trial protocol Appendix 3: Trial Organisation Appendix 4: Patient reported outcome questionnaires on health-related quality of life Appendix 5: Expected grass pollen season Appendix 6: COVID-19 pandemic measures

Clinical trial protocol	Date:	12-Nov-2021	
Trial ID: SU-G-01	Version:	4.0	
EudraCT No. 2020-000455-12	Status:	Final	
CONFIDENTIAL	Page:	11 of 77	•

Table of abbreviations

r	
AE	Adverse event
AIT	Allergy immunotherapy
ALT	Alanine aminotransferase
ARC	Allergic rhinoconjunctivitis
AST	Aspartate aminotransferase
BP	Blood pressure
CRA	Clinical research associate
CRO	Clinical research organisation
DMS	Daily medication score
DSS	Daily symptoms score
eCRF	Electronic case report form
EGPS	Entire grass pollen season
EMA	European medicines agency
ESI	Events of special interest
EudraCT	European Union drug regulating authorities clinical trials database
FAS	Full analysis set
FEV ₁	Forced expiratory volume in 1 second
FVC	Forced vital capacity
GCP	Good clinical practice
HAS	Haute Autorité de Santé
IB	Investigators brochure
ICH	International conference on harmonisation of technical requirements for registration of pharmaceuticals for human use
IEC	Independent ethics committee
IgE	Immunoglobulin E
IMP	Investigational medicinal product
IRB	Institutional review board
IRT	Interactive response technology
LABA	Long-acting B-agonist
LSLV	Last subject last visit
МАА	Marketing authorisation application

MAOIs	Monoamine oxidase inhibitors
MCID	Minimal clinically important difference
MedDRA	Medical dictionary for regulatory activities
MMRM	Mixed Model of Repeated Measurements
NPPs	Named patient products
PGPS	Peak grass pollen season
PP	Per protocol
QoL	Quality of life
QPPV	Qualified person responsible for pharmacovigilance
RCT	Randomised controlled trial
RQLQ	Rhinitis quality of life questionnaire
SABA	Short-acting β ₂ -agonist
SAE	Serious adverse event
SAP	Statistical analysis plan
SAS	Statistical analysis software; computer software for statistical programming
SCIT	Subcutaneous allergy immunotherapy
SDTM	Study Data Tabulation Model
SLIT	Sublingual allergy immunotherapy
SLIT-drops	Sublingual allergy immunotherapy drops
SLIT-tablet	Sublingual allergy immunotherapy tablet
SmPC	Summary of product characteristics
SOP	Standard operating procedure
SPT	Skin prick test
SRU	Standardized reactivity unit
SUSAR	Suspected unexpected serious adverse reactions
TEAE	Treatment emergent adverse events
TCS	Total combined score
WHO	World Health Organisation

Clinical trial protocol	Date:	12-Nov-2021	
Trial ID: SU-G-01	Version:	4.0	
EudraCT No. 2020-000455-12	Status:	Final	
CONFIDENTIAL	Page:	13 of 77	

Table of definitions

Anaphylaxis	The definition of anaphylaxis (Sampson H.A.et al. 2006) includes any 1 of the following 3 criteria:
	 Acute onset of an illness (minutes to several hours) with involvement of the skin, mucosal tissue, or both (e.g. generalised hives, pruritus, or flushing, or swollen lips, tongue, or uvula) AND either respiratory compromise (e.g. dyspnoea, wheeze-bronchospasm, stridor, reduced Peak Expiratory Flow (PEF), hypoxemia) or reduced BP* or associated symptoms of end-organ dysfunction (e.g. hypotonia [collapse], syncope, incontinence) Two or more of the following that occur rapidly after exposure to a likely allergen for the subject (minutes to several hours): a) Involvement of the skin-mucosal tissue (e.g. generalised hives, itch-flush, swollen lips, tongue, or uvula) b) Respiratory compromise (e.g. dyspnoea, wheeze-bronchospasm, stridor, reduced PEF, hypoxemia) c) Reduced BP* or associated symptoms (e.g. hypotonia [collapse], syncope, incontinence) d) Persistent gastrointestinal symptoms (e.g. crampy abdominal pain, vomiting) Reduced BP after exposure to known allergen for the subject (minutes to several hours): low systolic BP* or greater than 30% decrease in systolic BP
Completed	A randomised subject is considered completed if he/she has not discontinued the trial
Subject Completion date	For each completed subject, the date of the last scheduled procedure/end of trial visit
	(visit 9)
Concomitant medication	All medications being continued by a subject on entry into the trial and all medications given in addition to the background treatment during the trial
Date of last contact	Date of the last contact, either by telephone or in a visit
End of trial	The overall end of the trial is defined as the date of last follow-up phone visit (TC follow-up) for the last subject in the trial
Estimand	A precise description of the treatment effect reflecting the clinical question of interest posed by the trial objective. It summarises at a population-level what the outcomes would be in the same patients under different treatment conditions being compared (ICH 2020) .
Grass pollen season	 Start date: The first day of 3 consecutive days with (non-missing) pollen count larger than or equal to 10 grains/m3 Stop date: The last day before 3 consecutive days with (non-missing) pollen count less than 10 grains/m3 Peak: The 15 days period with the highest average pollen count during the entire grass pollen season
IMP	A pharmaceutical form of an active substance or placebo being tested or used as a reference in a clinical trial, including products with a marketing authorisation used or assembled (formulated or packaged) in a way different from the authorised form, or when used for an unauthorised indication, or when used to gain further information about the authorised form

Clinical trial protocol	Date:	12-Nov-2021	
Trial ID: SU-G-01	Version:	4.0	
EudraCT No. 2020-000455-12	Status:	Final	
CONFIDENTIAL	Page:	14 of 77	

Intercurrent events	Events occurring after treatment initiation that affect either the interpretation or existence of the measurements associated with the clinical question of interest. It is necessary to address intercurrent events when describing the clinical question of interest in order to precisely define the treatment effect that is to be estimated (ICH 2020).
IRT	Automated system to be used for managing randomisation, subject enrolment and trial supply management in this trial
LSLV	Last scheduled physical visit for any subject (visit 9)
Life-threatening asthma	Asthma worsening that requires intubation and/or is associated with hypercapnia requiring non-invasive ventilator support
Primary completion date	Date of the last data collection for the primary endpoint (ClinicalTrials.gov) is the last scheduled physical visit for any subject (visit 9)
Rescue medication	Medicinal products provided by ALK when the efficacy of the IMP is not sufficient or likely to cause an adverse event (AE) to the subject or to manage an emergency situation in relation to grass pollen allergy symptoms in agreement with the EMA Definition of IMPs and Use of AMPs Consultation Document (EMA 2016) The rhinoconjunctivitis rescue medication in this trial is:
	Antinistamine tablets Antihistomine ave drang
	Anunistamine eye drops Ordinastensid asset asset
	Conticosteroid hasai spray
Source documents	Source documents are original documents, data, and records from which the subjects' electronic case report form (eCRF) data are obtained. These include, but are not limited to, hospital records (from which medical history and concomitant medication may be summarised into the eCRF), clinical and office charts, laboratory and pharmacy records, diaries, microfiches, radiographs, and correspondence
Systemic corticosteroids	Oral, intramuscular, or intravenously administered corticosteroids
TEAE	TEAEs are defined as adverse events with start date and/or time on or after the time of first IMP administration and no later than 7 days after last IMP administration
Trial completion	The trial is completed once the integrated clinical trial report (ICTR) is signed
Trial discontinuation date	Date of subject trial discontinuation. In case of subjects lost to follow-up, the discontinuation date is defined as the date the investigator/sponsor decides to discontinue the subject

Protocol versions

Date	Version	Description of document	Rationale for amendment
29-Jan-2020	1.0	Final Protocol	N/A
11-Mar-2020	2.0	Final Protocol	Version update to align with IB
23-Oct-2020	3.0	Final Protocol	 Key changes: To address EMA recommendations in the 'Guidance on the Management of Clinical Trials during the COVID-19 (Coronavirus) pandemic' (EMA 2020) FEV₁ removed from screening visit 1 and from subsequent visits after randomisation visit 2 Oropharyngeal exam removed from screening visit 1 and from subsequent visits after randomisation visit 2 Addition of retention TC between visits V5 and V6 Removal of visit schedules/content from section 10. This section is not mandatory, is repetitive to the flow chart and assessments and creates a risk for error Estimand has been added as per ICH E9 (R1) addendum on estimands and sensitivity analysis in clinical trials to the guideline on statistical principles for clinical trials (Step 5) (ICH 2020)
12-Nov-2021	4.0	Final Protocol	 Key changes List of appendices updates Flowchart: Time window for V4 and V7 expanded to allow up to 14 days prior to EGPS. Footnote 1 updated with 'optional' referring to TC1 and updated year of randomisation to 2021. 3.4: End of trial definition updated to the date of the last follow-up phone visit (TC follow-up) for the last subject in the trial. 7.: Table 2 updated due to reassessment of criticality of restricted and prohibited concomitant medication. 11.4: clarification on stratification added to medical history: A subject should be stratified as asthmatic if they have been diagnosed and/or treated for asthma in adulthood. 11.14: Assessments reordered to ease readability 12.1: Deletion of bullet stating that events defined as efficacy endpoints should not be recorded as AEs. 12.1: Addition of bracket in sentence: Selected AEs (nonserious or serious) will be considered ESIs 12.3 and 12.3.1 Specification of ESI forms and procedures 15.11.4 Correction of undefined reference Appendix 3 updated due to change of central lab and CRO legal entity and contact details

EudraCT No. 2020-000455-12Status:FinalCONFIDENTIALPage:16 of 77

Flow chart

Visit ID:	Protocol section	V1	V2	TC1	∨3	V4	V5	TC2	V6	V7	V8	V9	TC Follow- up	Unsched- uled visit
Visit: V=Site Visit TC=Telephone Contact		Screening	Random- isation	Optional between V2 and V3 ¹	1 st off- season	1 st pre- EGPS ²	1 st on- season	Retention between V5 and V6	2 nd off- season	2 nd pre- EGPS ²	2 nd on- season	End of trial	Post- treat- ment	
Time Window		At least 3 days before V2	At least 16 weeks before start of 1 st EGPS ²	November 2021	January 2022	14 to 0 days before start of 1st EGPS ²	7 to 0 days before expected PGPS ³	4-12 weeks before V6	January 2023	14 to 0 days before start of 2 nd EGPS ²	7 to 0 days before expected PGPS ³	1 to 7 days from end of 2 nd EGPS ²	4 to 10 days after V9	As necessary
Informed consent	11.1	х												
Demography and body measurements	11.3	х												
Smoking habits	11.5	х												
Medical history	11.4	х												
In-/exclusion criteria	4.1/4.2	х	х											
Randomisation	6		х											
Urine pregnancy test ⁴	11.10	(X)	(X)		(X)	(X)	(X)		(X)	(X)	(X)	(X)		(X)
Physical examination	11.8	Х										х		(X)

¹ An optional retention telephone contact for those subjects randomised between start of August and end of November 2021

² EGPS- entire grass pollen season (see Appendix 5)

³ PGPS- peak grass pollen season (see Appendix 5)

⁴ For females of child-bearing potential, urine pregnancy tests should be performed at each visit and if a menstrual period is missed.

Clinical trial protocol Trial ID: SU-G-01 EudraCT No. 2020-000455-12 CONFIDENTIAL

Visit ID:	Protocol section	V1	V2	TC1	V3	V4	V5	TC2	V6	V7	V8	V9	TC Follow- up	Unsched- uled visit
Visit: V=Site Visit TC=Telephone Contact		Screening	Random- isation	Optional between V2 and V3 ¹	1 st off- season	1 st pre- EGPS ²	1 st on- season	Retention between V5 and V6	2 nd off- season	2 nd pre- EGPS ²	2 nd on- season	End of trial	Post- treat- ment	
Oropharyngeal examination	11.8		х											(X)
Vital signs	11.12	Х	х		х	х	Х		х	х	х	Х		(X)
Lung function test	11.7		х											(X)
Blood and urine samples for safety laboratory assessments	11.13	х										x		(X)
Blood sample for specific IgE	11.14	Х												
	11.14	х			x	х			x			x		(X)
Blood sample for biobanking⁵	11.15	(X)										(X)		
SPT	11.11	Х	(X)											(X)
Intake of IMP at clinic	9.1/9.2		х											
Instruct the subject in use of IMP	9.1/9.2		х											
Record previous and concomitant medication	11.6	х	х	х	x	х	х	х	х	x	х	х	х	x
Assess and/or record AEs	12.2	х	х	Х	х	х	Х	Х	х	х	Х	х	Х	х
Assess eosinophilic eosophagitis	11.9	Х	Х		Х	х	Х		х	х	Х	х		(X)
Dispense IMP	8.1		х		Х	х	Х		х	Х	Х			(X)

⁵ Only if biobanking specific informed consent has been signed and according to country specific regulations.

Clinical trial protocol Trial ID: SU-G-01 EudraCT No. 2020-000455-12 CONFIDENTIAL

Visit ID:	Protocol section	V1	V2	TC1	V3	V4	V5	TC2	V6	V7	V8	∨9	TC Follow- up	Unsched- uled visit
Visit: V=Site Visit TC=Telephone Contact		Screening	Random- isation	Optional between V2 and V3 ¹	1 st off- season	1 st pre- EGPS ²	1 st on- season	Retention between V5 and V6	2 nd off- season	2 nd pre- EGPS ²	2 nd on- season	End of trial	Post- treat- ment	
Dispense rescue medication	8.2					х	(X)			(X)	(X)			(X)
Trial medication collection, compliance check compliance and drug accountability	8.5				x	x	x		x	x	x	x		x
	11.17		х									х		
Issue and instruct in use of E- diary/LogPad	11.16				x									
Instruct in use of E- diary/LogPad	11.16					x	(X)			x	(X)			
eDiary completion:	11.16.5						X ₆							
eDiary completion: • RQLQ	11.16.4				х	X	X ⁷			X	X ⁷			
eDiary completion: • Symptoms • Medication	11.16.1/ 11.16.2					x	X ⁷			x	X ⁷			
eDiary completion:	11.16.3					x	X ⁷			x	X ⁷			
Review eDiary recordings	11.16						Х		х	Х	Х	Х		(X)
Collect eDiary												x		

⁶ The second will be performed at the defined end of the EGPS for each region (see Appendix 5)

⁷ Rhinoconjunctivitis symptoms scores, use of rescue medication and will be collected daily and RQLQ will be collected weekly during the EGPS until the defined end of the EGPS for each region (see Appendix 5)

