12 SAFETY PROCEDURES

Information about AEs, whether reported by the subject, discovered by the investigator by reviewing eDiary records, detected through physical examination, laboratory test or other means, must be collected and recorded on the AE form and followed up as appropriate. Evaluation of AEs including severity, causality, outcome and seriousness assessments must be performed by a physician.

Any AE occurring from the time the informed consent was signed by the subject and until the last follow-up phone contact must be recorded and reported on the AE page in the eCRF. This includes all AEs, even AEs occurring before the subject is administered the IMP and whether or not AEs are observed in connection with the trial assessments and conduct of the trial.

Clinical trial protocol	Date:	12-Nov-2021			
Trial ID: SU-G-01	Version:	4.0		1	
EudraCT No. 2020-000455-12	Status:	Final			
CONFIDENTIAL	Page:	49 of 77	_		

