12.3 Collection, recording and reporting of AEs

AEs must be recorded on the AE form in the eCRF with the initial eCRF report containing as much information as possible. One single AE form must be used per AE from start to resolution. For SAEs and ESIs, additional information will be collected. For each of the 4 pre-defined ESIs, the

Clinical trial protocol	Date:	12-Nov-2021	
Trial ID: SU-G-01	Version:	4.0	
EudraCT No. 2020-000455-12	Status:	Final	
CONFIDENTIAL	Page:	51 of 77	

investigator must fill out a specific eCRF ESI form with additional questions, in order to ensure that all relevant data is captured.

If the same type of AE occurs more than 1 day in a row with the same pattern (e.g. itching in the mouth for 5-10 minutes after intake of IMP) it is considered a recurrent AE. The AE form should be filled in with the start date and the description. If the AE no longer reoccurs after IMP intake, the AE form should be completed with a stop date. If the AE then re-appears on a subsequent day, a new AE form should be filled in.

The investigator should record the diagnosis, if available. If no diagnosis is available, the investigator should record each sign and symptom as individual AEs. Further, the diagnosis of the underlying disease should be reported instead of a procedure performed due to the disease (e.g. if a subject undergoes surgery due to appendicitis, appendicitis, and not the surgery performed, should be reported as the AE).

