12.3.2 Follow-up on AEs and SAEs

SAEs must be followed up until resolution and until all queries have been resolved. The investigator must respond to SAE follow-up requests from ALK without delay and no later than 7 days after receiving the request.

For chronic diseases ongoing SAEs can be closed at the end of trial (visit 9) with the term "not recovered" (as evaluated upon medical evaluation by the investigator or the sponsor).

Clinical trial protocol	Date:	12-Nov-2021	
Trial ID: SU-G-01	Version:	4.0	
EudraCT No. 2020-000455-12	Status:	Final	
CONFIDENTIAL	Page:	52 of 77	

The investigator must ensure that the worst-case severity and seriousness of an event is kept throughout the trial.

Non-serious AEs must be followed up until resolution or until the end of trial (visit 9).

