Primary trial completion date	Date of the last data collection for the primary endpoint (ClinicalTrials.gov) is the last scheduled physical visit for any subject (V9).
Rescue medication	Medicinal products provided by ALK when the efficacy of the IMP is not sufficient or likely to cause an AE to the subject or to manage an emergency situation in relation to grass pollen allergy symptoms in agreement with the EMA Definition of IMPs and Use of AMPs Consultation Document (EMA 2016)
	The rhinoconjunctivitis rescue medication in this trial is:
	Antihistamine tablets
	Antihistamine eye drops
	Corticosteroid nasal spray.
Source documents	Source documents are original documents, data, and records from which the subjects' electronic case report form (eCRF) data are obtained. These include, but are not limited to, hospital records (from which medical history and

	concomitant medication may be summarised into the eCRF), clinical and office charts, laboratory and pharmacy records, diaries, microfiches, radiographs, and correspondence.
Systemic corticosteroids	Oral, intramuscular, or intravenously administered corticosteroids.
TEAE	TEAEs are defined as AEs with start date and/or time on or after the time of first IMP administration and no later than 7 days after last IMP administration.
Trial completion	The trial is completed once the CSR is signed.
Withdrawal from trial date	Date of subject withdrawal from trial. In case of subjects lost to follow-up, the withdrawal date is defined as the date the investigator/sponsor decides to withdrawal the subject.

3 Introduction

The SAP supplements the statistical section in the protocol and provides additional details regarding estimands, analysis sets, endpoints and statistical analyses. In Section 9.1 detailed descriptions of pollen seasons, derivation of endpoints, imputation of dates, and the statistical analyses are provided. In supplementary document to the SAP: Documentation of Trial Analysis Sets, the various subject related listings are provided.

Changes to the analyses and changes that might (or can) impact the analyses described in the protocol are documented in Section 6.5.

This SAP has been written and approved before database lock and unblinding.

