6.4.2.1 Events of special interest

An AE is any untoward medical occurrence in a subject that does not necessarily have a causal relationship with the administered IMP. An AE is a TEAE if the time of onset is on or after the time of the first dose administration of IMP and, no later than seven days seven days after the last dose administration of IMP. Selected (non-serious or serious) AEs are considered ESIs. ESIs are events that are considered critical for the evaluation of the product's safety profile and for which additional data was collected. ESIs for this trial are:

- Systemic allergic reactions including anaphylaxis
- Events treated with adrenaline
- Severe local swelling of the mouth and/or throat
- Eosinophilic oesophagitis.

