Serious TEAEs, severe TEAEs, TEAEs leading to IMP discontinuation, IMP-related TEAEs leading to IMP interruption, individual ESIs, TEAEs, and all non-treatment-emergent AEs for the total analysis set will be listed. Medication errors will also be listed. Pregnancies will be listed if fewer than 10 cases have been reported; otherwise summarised.

 Date:
 27-Oct-2023

 Version:
 1.0

 Status:
 Final

 Page:
 31 of 47

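### Treatment-emergent status depends on onset date alone, so an AE that begins between consent and first dose and worsens on IMP is missing from every TEAE-based by-arm table

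*Protocol*

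**What the plan says.** The definition appears three times, each time by onset only. The protocol's table of definitions has "TEAEs are defined as adverse events with start date and/or time on or after the time of first IMP administration", SAP section 2 has "TEAEs are defined as AEs with start date and/or time on or after the time of first IMP administration", and SAP 6.4.2.1 has "An AE is a TEAE if the time of onset is on or after the time of the first dose administration of IMP". All three close the window seven days after the last dose. None mentions an event already present that gets worse.

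Collection starts earlier. Protocol section 12 records AEs from the signing of consent: "This includes all AEs, even AEs occurring before the subject is administered the IMP". Protocol 12.3 adds "One single AE form must be used per AE from start to resolution", and its only instruction to open a further form is for a recurrent event that has stopped and then comes back. Protocol 12.3.2 requires that "worst-case severity and seriousness of an event is kept" throughout the trial.

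The only rule on worsening is in protocol 12.1. It makes worsening of a pre-existing condition documented as medical history a reportable AE. Significant findings present at screening also go to medical history (protocol 11.8 and 11.12 for physical examination and vital signs, 12.3.4 for laboratory events).

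SAP 6.4.2.2 builds its main by-arm AE tables from TEAEs. For the rest it says "all non-treatment-emergent AEs for the total analysis set will be listed".

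**The concern.** Worsening on treatment is part of what a by-arm safety comparison should show. Under the written rules, whether it is tabulated depends on when the condition first appeared. If it was present before consent and recorded as history, worsening on IMP is a new AE with an on-treatment onset. If it appeared a day after consent, the same worsening is a change of grade on an existing form with a pre-dose start date. No reason is given for treating the two differently.

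The rows affected include severe TEAEs and TEAEs leading to IMP discontinuation. Where such rows hold few events, one or two misclassified events can visibly change them. The listing would also mislead: because the form keeps the worst grade, an event that became severe on IMP could appear there as a severe event that began before treatment.

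**Working it through.** The plan states no figure to reproduce, so the check is of the rule and of the outputs built on it.

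**Rule.** An AE is a TEAE if first dose ≤ onset ≤ last dose + 7 days. With invented dates (first dose 1 Sep 2021, last dose 1 Aug 2023):

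- AE begins 25 Aug 2021, in screening, and worsens on IMP on its single form: onset precedes first dose, so **not a TEAE**.
- Medical-history condition worsens on 20 Sep 2021 and is recorded as a new AE under protocol 12.1: **TEAE**.
- AE begins on the day of first dose, at or after dosing: **TEAE**.

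Only the first case is lost. It is the fixed start date that removes the event. The worst-grade rule adds a second difficulty: the form need not show when the worsening happened.

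**Outputs.** Taking the first case through each planned output:

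| Output | Limited to TEAEs? | Event shown by arm? |
|---|---|---|
| SAP 6.4.2.2 overall summaries (all and IMP-related) | Yes | No |
| SAP 6.4.2.2 SOC/PT tables (all and IMP-related) | Yes | No |
| SAP 6.4.2.2 severe TEAEs; TEAEs leading to discontinuation; IMP-related TEAEs leading to interruption | Yes | No |
| SAP 6.4.2.2 overall safety-profile table, including ESIs | Yes | No |
| SAP 6.4.2.2 SAE summary | Not in that sentence; yes in the SAP 3.1 endpoint and in the later list of serious events | Unclear |
| SAP 8.3 disposition (reasons for stopping IMP) | No | Only if the subject stopped, and only as a reason |
| Protocol 15.12.1 AE summary | No, but detail is left to the SAP | Only if the SAP carried it out as written |
| SAP 6.4.2.2 non-treatment-emergent AEs | Not applicable | Listed only |

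**A related mismatch.** SAP 6.1.2 classifies discontinuation due to an IMP-related AE with no treatment-emergent condition, and SAP 3.1 says that the endpoint of TEAEs leading to discontinuation uses those same definitions. A subject could therefore be in the IMP-related AE category for the estimand and absent from the table of TEAEs leading to discontinuation.

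**Length of the exposed period.** The protocol flow chart sets screening at least 3 days before randomisation and gives no upper limit. SAP Table 1 has the first visit on 02-May-2021 and the last randomisation on 31-Dec-2021. SAP 3.2 prints the first randomisation as 15-Aug-2022, which cannot precede that last date. If the year is read as 2021 (an assumption), 02-May to 15-Aug is 105 days, or 105 / 7 = 15 weeks. That is a ceiling for the earliest-screened subjects, not a typical interval.

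**The case against.** The strongest reply is that very few events can fall into the gap. Conditions and findings present at screening go to medical history, so their worsening is already captured. Grass rhinoconjunctivitis is itself an entry requirement, so a long screening period over the 2021 season adds little. Exclusion E12 and protocol 9.2 keep subjects with current infections, and 9.2 those with severe oral inflammation, from starting IMP at that point. Nothing is lost from the data either: the event stays on its form and in a listing, and SAE reporting and safety surveillance still apply. All of this stands and limits the size of the point. It does not close the gap, because protocol 9.2 asks for infections to have improved, not resolved, and nothing prevents other screening-onset AEs from continuing into dosing.

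Three stronger readings are tempting and are not supported.

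- *That the event vanishes from every by-arm safety table.* It does not: the SAE sentence in SAP 6.4.2.2 carries no treatment-emergent limit, and SAP 8.3 tabulates reasons for stopping IMP by arm whatever the AE's onset.
- *That a count can be given.* One could assume that 5–15% of the 445 randomised had an AE ongoing at first dose (445 × 0.05 = 22; 445 × 0.15 = 67) and that 10–20% of those worsened (22 × 0.10 = 2; 67 × 0.20 = 13). Neither rate has any basis in the documents, and the result would mix all grades and both arms. Nor does the threshold of 10 events in SAP 6.4.2.2 forecast how many severe events there will be; it only decides between a listing and a table.
- *That the comparison is biased in favour of active treatment.* Counts are understated in whichever arm the worsening occurs. The effect on the difference between arms cannot be known from the plan.

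**Conclusion.** The point holds in a limited form. The TEAE definition has no worsening limb, and with one form and one start date per AE, a screening-onset event that worsens or becomes serious on IMP falls outside every TEAE-based by-arm table. This is at odds with how the protocol treats worsening of medical-history conditions. It is also at odds with SAP 9.4.1, which resolves partial dates in favour of treatment-emergent status unless the information rules it out.

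The number of events affected cannot be computed, because the documents give no screening-period AE rate; it is probably small. The conclusion assumes that sites followed the single-form instruction. A site that opened a new form at worsening would have produced a TEAE, but nothing in the protocol asks for that. Separately, the SAP disagrees with itself on whether the SAE summary is limited to treatment-emergent events. The correction is worth making because it is cheap and affects rows where single events matter.

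**What to change.** 1. In SAP section 2 and 6.4.2.1, define a TEAE as an AE that begins on or after first IMP, or that was present before first IMP and increases in severity or becomes serious on or after it, keeping the existing seven-day limit after the last dose.
2. The form may not date the worsening, so identify AEs ongoing at first dose from their start and stop dates and show them by arm in a separate row. Count as TEAEs those that can be shown to have worsened or become serious on IMP, and those assessed as IMP-related or that led to stopping IMP. Do not reclassify all of them by default, since that would count events that never worsened.
3. State in SAP 6.4.2.2 whether the SAE summary is limited to treatment-emergent events, so that it agrees with the endpoint in SAP 3.1 and with the list of serious events later in 6.4.2.2.
4. For future trials, have protocol 12.3 require a new AE record when an event that began before first dose worsens after it. That is the cleaner way to collect the information, but the last visit here was 22-Sep-2023, so it cannot change data already collected.

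The cost is a few lines of SAP text, a small programming change and a short blinded review of AEs ongoing at first dose. A few more TEAEs would be counted in both arms. The SAP states that it was approved before database lock and unblinding. If unblinding has since taken place, report the change as a departure from the SAP in the trial report, as protocol section 15 provides.
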